- b) Previous diagnosis of monogenic etiology of Type 2 diabetes such as maturity onset diabetes of the young (MODY), genetic disorders with strong associations with insulin resistance/diabetes and/or obesity such as Turner's Syndrome and Prader-Willi, or secondary diabetes (steroid use, Cushing's disease, acromegaly), secondary diabetes mellitus, or diabetes insipidus.
- c) Diabetes ketoacidosis within 6 months of screening
- d) Current use of the following medications for the treatment of diabetes, or use within the specified timeframe prior to screening for the main study:
 - Eight weeks: sulfonylureas, alpha glucosidase inhibitors, metiglinide, oral or injectable incretins or incretin mimetics, other anti-diabetes medications not otherwise specified
 - Sixteen weeks: thiazolidinediones. DPP-4 inhibitors (with no reported medication related AEs related to DPP-4 inhibitors), sodium glucose cotransporter-2 (SGLT-2) inhibitors (with no reported medication related AEs related to SGLT-2 inhibitors)

Study Drug: includes both Investigational [Medicinal] Products (IP/IMP) and Non-investigational [Medicinal] Products (Non-IP/Non-IMP) as listed:

Table 2: Study Drug for BMS-477118 AND BMS-512148

| Medication | Potency | IP/Non-IP |
|---|---------|-----------|
| Saxagliptin | 2.5 mg | IP |
| Saxagliptin | 5 mg | IP |
| Dapagliflozin | 5 mg | IP |
| Dapagliflozin | 10 mg | IP |
| Placebo Matching Saxagliptin 2.5 mg/5mg | 0 mg | IP |
| Placebo Matching Dapagliflozin 5 mg | 0 mg | IP |
| Placebo Matching Dapagliflozin 10 mg | 0 mg | IP |

Statistical Considerations:

Sample Size:

The sample size for this study was selected to be consistent with the research hypotheses.

Dapagliflozin and saxagliptin will be compared with placebo separately. No comparisons between dapagliflozin and saxagliptin will be performed.

The sample size for this study is based on the ability to detect a 0.75% improvement over placebo for dapagliflozin or saxagliptin in change from baseline in HbA1c at Week 26 (ST) with approximately 80% power for each comparison at a 2-sided alpha level of 0.05. If 243 pediatric subjects are randomized and analyzed, and each treatment compared to placebo at a 2-sided alpha=0.05 level, this will provide approximately 80% power for each comparison to detect a 0.75% reduction in HbA1c change from baseline versus placebo assuming a standard deviation of 1.7%.

Day 1 Randomization will be stratified based on the baseline anti-diabetic treatment regimen (stable baseline dose of metformin [IR or XR]), a stable baseline dose of insulin, or a stable combination of metformin [IR or XR] and insulin), gender, and age (10 to below 15 years of age, 15 to below 18 years of age).

The standard deviation estimate of 1.7% is based on a blinded review of the ongoing study data.

Endpoints:

Primary Endpoint:

Change from baseline in HbA1c at Week 26

Secondary Endpoints:

- Change from baseline in FPG at Week 26
- Percentage of subjects with baseline HbA1c ≥ 7% who achieve an HbA1c level < 7.0% at Week 26

Exploratory Endpoints:

Exploratory efficacy endpoints for short-term assessment of saxagliptin and dapagliflozin

 Percentage of subjects who require glycemic rescue medication or discontinue the study medication due to lack of efficacy during the 26-week treatment period

Time to initiation of glycemic rescue medication or discontinuation of study medication due to lack of efficacy during the 26-week treatment period

Exploratory efficacy endpoints for long-term assessment of saxagliptin and dapagliflozin:

- Change from baseline in HbA1c at Week 52
- Change from baseline in FPG at Week 52
- Percentage of subjects with baseline $HbA1c \ge 7\%$ who achieve an HbA1c level < 7% at Week 52
- Time to initiation of glycemic rescue medication or discontinuation of study medication due to lack of efficacy during the 52-week treatment period

Exploratory efficacy endpoints for monotherapy assessment of saxagliptin and dapagliflozin:

- Change in HbA1c during the randomized withdrawal period
- Change in FPG during the randomized withdrawal period
- Percentage of subjects who achieve or maintain a HbA1c level < 7.0% at the end of the randomized withdrawal period
- Time to initiation of glycemic rescue medication or discontinuation of study medication due to lack of efficacy using the start time of randomized withdrawal as the reference point

Safety Endpoints:

Safety endpoints consist of the incidence of AEs, SAEs, hypoglycemic events, discontinuations due to AEs, marked abnormalities in clinical laboratory tests, vital signs, Tanner staging, measures of growth and maturation, DKA events, and safety laboratory tests.

Analyses:

Dapagliflozin and saxagliptin will be summarized separately. A common placebo group will be included in each summary.

In addition, within the analyses of dapagliflozin and saxagliptin, the overall (combined low-dose and high-dose) efficacy and safety analyses will be repeated for the subgroup of subjects on a stable baseline dose of metformin (IR or XR) (with or without insulin). For these analyses, the dapagliflozin and saxagliptin regimens within each treatment will be combined into one subgroup and compared to the corresponding (common) placebo subgroup. P-values corresponding to subgroup comparisons will be reported for the primary and secondary efficacy endpoints, and will be reported at the nominal significance level.

All efficacy analyses will be performed using the Randomized Subjects Data Set (all randomized subjects who receive at least one dose of study medication during the treatment period) unless otherwise specified. Furthermore, to account for randomization withdrawal, analyses dedicated to monotherapy assessment will be performed on the Randomized Withdrawal Subjects Data Set.

The following treatment regimens are considered for analysis:

- Low-dose/high-dose: Initial treatment of the low-dose followed by up-titrating to the high-dose for those who do not achieve the glycemic target of HbA1c < 7% at Week 12 and continuing treatment with the low-dose for those achieving the glycemic target of HbA1c<7% at Week 12
- Low-dose: Initial treatment of the low-dose followed by continuing treatment on the low-dose drug for those who do not achieve the glycemic target of HbA1c <7% at Week 12 and continuing treatment with the low-dose for those achieving the glycemic target of HbA1c < 7% at Week 12

Revised Protocol No: 06

Following the third randomization:

- Subjects initially randomized to dapagliflozin (or saxagliptin) with metformin as background therapy will be re-randomized in a 1:1 ratio to either dapagliflozin (or saxagliptin) alone or to dapagliflozin (or saxagliptin) with metformin as background therapy
- Subjects initially randomized to placebo with metformin as background therapy will be re-randomized in a 1:1:1 ratio to dapagliflozin alone or saxagliptin alone or placebo with metformin as background therapy

For each drug, the comparison vs placebo will be tested at a two-sided alpha level of 0.05.

The primary efficacy analysis will be performed using an analysis of covariance (ANCOVA). For this analysis, all dose levels for a treatment will be combined into one treatment group for each drug. Separate models will be used for saxagliptin and dapagliflozin analyses, and each analysis will include the (common) placebo control. Each model will have terms for baseline value, treatment group, and randomization strata. Point estimates and 95% confidence intervals will be calculated based on maximum likelihood for the adjusted mean changes within each treatment group as well as for the differences in adjusted mean changes between treatment groups.

The intent-to-treat estimand (which will be estimated using all available data regardless of premature treatment discontinuation and regardless of rescue therapy initiation) will be evaluated as the primary estimand. Missing values for Week 26 will be imputed using a multiple imputation method assuming the data are not missing at random. Multiple imputation using retrieved drop-outs will be used if there is sufficient data from 'retrieved drop-outs', defined as subjects who discontinued the treatment (but not the study) and had a Week 26 HbA1c value. The details of the imputation methods will be presented in the statistical analysis plan.

To assess the robustness of the primary efficacy analysis for the change in HbA1c from baseline to Week 26, additional sensitivity analysis may be performed using the Evaluable Subjects Data Set if > 10% of the subjects in any treatment group in the Randomized Subjects Data Set have relevant protocol deviations.

The primary endpoint will also be compared between the low-dose/high-dose treatment regimen and placebo, separately for both dapagliflozin and saxagliptin. In addition, up-titrating to high-dose and continuing on low-dose will be compared in the subset of dapagliflozin and saxagliptin subjects who had $HbA1c \ge 7\%$ at Week 12. These analyses are described under secondary efficacy analyses.

Secondary efficacy analyses will also be performed separately for each drug (dapagliflozin and saxagliptin). For each drug, the following sequential testing order will be employed to control multiplicity of testing for the secondary objectives.

- Comparison of mean reduction in HbA1c from baseline at Week 26 between the low-dose/high-dose treatment regimen and placebo
- Comparison of mean reduction in HbA1c from baseline at Week 26 between the low-dose treatment regimen and placebo
- Comparison of mean reduction in FPG from baseline at Week 26 between overall drug treatment (all doses and regimens combined) and placebo
- 4. Comparison of mean reduction in FPG from baseline at Week 26 between the low-dose/high-dose treatment regimen and placebo
- Comparison of mean reduction in FPG from baseline at Week 26 between the low-dose treatment regimen and placebo
- 6. Comparison of the percentage of subjects with baseline HbA1c ≥7% who achieve an HbA1c level < 7.0% at Week 26 between overall drug treatment (all doses and regimens combined) and placebo
- 7. Comparison of the percentage of subjects with baseline HbA1c ≥ 7% who achieve an HbA1c level < 7.0% at Week 26 between the low-dose/high-dose treatment regimen and placebo
- 8. Comparison of the percentage of subjects with baseline HbA1c ≥ 7% who achieve an HbA1c level < 7.0% at Week 26 between the low-dose treatment regimen and placebo
- 9. Comparison of mean reduction in HbA1c from baseline at Week 26 between the high-dose and the low-dose in subjects who do not achieve an HbA1c < 7% at Week 12

Revised Protocol No: 06

- 10. Comparison of mean reduction in FPG from baseline at Week 26 between the high-dose and the low-dose in subjects who do not achieve an HbA1c < 7% at Week 12
- 11. Comparison of the percentage of subjects with baseline HbA1c ≥ 7% who achieve an HbA1c level < 7.0% at Week 26 between the high-dose and the low-dose in subjects who do not achieve an HbA1c < 7% at Week 12

For each drug, a weighted ANCOVA will be performed for the change from baseline in HbA1c at Week 26 to compare the placebo and the low-dose/high-dose treatment regimen. For this analysis, all dapagliflozin and saxagliptin subjects who had HbA1c <7% at Week 12 and remained on the low-dose will get a weight of one. The dapagliflozin and saxagliptin subjects who had HbA1c \geq 7% at Week 12 and continued on the low-dose will get a weight of 0. The dapagliflozin and saxagliptin subjects who had HbA1c \geq 7% at Week 12 and received the high-dose will get a weight of 2. All subjects who do not undergo the second randomization and all placebo subjects will get a weight of one.

For each drug, a weighted ANCOVA will be performed for the change from baseline in HbA1c at Week 26 to compare the placebo and the low-dose treatment regimen. For this analysis, all dapagliflozin and saxagliptin subjects who had HbA1c < 7% at Week 12 and remained on the low-dose will be get a weight of one. The dapagliflozin and saxagliptin subjects who had HbA1c \geq 7% at Week 12 and continued on the low-dose will get a weight of 2. The dapagliflozin and saxagliptin subjects who had HbA1c \geq 7% at Week 12 and received the high-dose will get a weight of 0. All subjects who do not undergo the second randomization and all placebo subjects will get a weight of one.

For subjects on dapagliflozin and saxagliptin who had $HbA1c \ge 7\%$ at Week 12, the change from baseline HbA1c at Week 26 (ST) will be compared between the subjects re-randomized to remain on the low-dose and the subjects who are re-randomized to the high-dose using an ANCOVA. This analysis will be based on the Up-titration Randomized Subjects Data Set.

Change from baseline at Week 26 (ST) in FPG will be analyzed similarly as the analyses of change from baseline in HbA1c at Week 26.

The proportion of subjects achieving HbA1c < 7.0% at Week 26 (ST) will be analyzed using weighted logistic regression with adjustment for the baseline HbA1c measurement and the randomization strata. Weighting for the subjects will be applied similarly to a weighting in the analysis of change from baseline in HbA1c. Subjects with missing a response at Week 26 will be imputed by dichotomizing the imputed values of HbA1c at Week 26.

The assessment of safety will be based on the analyses of AEs, vital signs, physical examinations, electrocardiograms, hypoglycemia events, DKA events, safety laboratory evaluations, and measures of growth and maturity. Dapagliflozin and saxagliptin will be summarized separately. Both low-dose and high-dose saxagliptin and dapagliflozin groups, respectively, will be combined for saxagliptin and dapagliflozin to provide the safety summary for overall saxagliptin and overall dapagliflozin compared to placebo. A common placebo group will be included in each summary.

Measures of growth, bone, and maturation markers will be summarized for ST and the combined ST+LT treatment periods. Exploratory analyses will be performed for overall saxagliptin and overall dapagliflozin separately, by combining all low-dose and high-dose treatment groups as appropriate. All analyses will be conducted on the Randomized Subjects Data Set.

Exploratory analyses for the monotherapy period will include only subjects who are on background medication with metformin and have HbA1c measurement < 7.5% at Week 26 or Week 32.

The monotherapy safety assessment will include standard safety assessments occurring during the randomized withdrawal period. These analyses will be conducted during the randomized withdrawal period using the Randomized Withdrawal Subject Data Set. Exploratory efficacy and safety analyses will include short and long-term assessment of saxagliptin and dapagliflozin, and monotherapy assessment.

THIRD RANDOMIZATION (WEEK 32 OR WEEK 40)b WEEK 26 or WEEK 32a STUDY DRUG ELIGIBILITY RANDOMIZATION & TREATMENT RANDOMIZED 1:1: TO EITHER: ELIGIBLE BASED ON HbA1c < 7.5% AND DISCONTINUE METFORMIN AND UP-TITRATE TO HIGH BACKGROUND MEDICATION OF DOSE OF SAXAGLIPTIN (5mg) OR DAPAGLIFLOZIN (10mg) DRUG METFORMIN ONLY LOW DOSE OR CONTINUE METFORMIN AND CURRENT TREATMENT Saxagliptin 2.5mg or Dapagliflozin 5mg NO THIRD RANDOMIZATION NOT ELIGIBLE BASED ON CONTINUE BACKGROUND MEDICATION AND BACKGROUND MEDICATION DRUG LOW DOSE RANDOMIZED 1:1: TO EITHER: DRUG ELIGIBLE BASED ON HbA1c < 7.5% AND DISCONTINUE METFORMIN AND CONTINUE HIGH DOSE OF Subjects HIGH BACKGROUND MEDICATION OF SAXAGLIPTIN OR DAPAGLIFLOZIN with DOSE METFORMIN ONLY HbA1c **OR** CONTINUE METFORMIN AND CURRENT TREATMENT Saxagliptin < 7.5% 5mg or Dapagliflozin 10mg NO THIRD RANDOMIZATION NOT ELIGIBLE BASED ON CONTINUE BACKGROUND MEDICATION AND BACKGROUND MEDICATION DRUG HIGH DOSE RANDOMIZED 1:1:1 TO EITHER: DISCONTINUE METFORMIN AND SWITCH TO: ELIGIBLE BASED ON HbA1c < 7.5% SAXAGLIPTIN HIGH DOSE (5mg) OR AND BACKGROUND MEDICATION OF DAPAGLIFLOZIN HIGH DOSE (10mg) METFORMIN ONLY PLACEBO OR CONTINUE METFORMIN AND PLACEBO NOT ELIGIBLE BASED ON NO THIRD RANDOMIZATION CONTINUE ON BACKGROUND MEDICATION AND PLACEBO BACKGROUND MEDICATION All subjects with NO THIRD RANDOMIZATION NOT ELIGIBLE BASED ON HbA1c ≥ 7.5% CONTINUE ON BACKGROUND MEDICATION AND CURRENT HbA1c ≥ 7.5% at Week 26 and Week 32 TREATMENT

Figure 4: Subgroups following the third randomization at Week 32 or Week 40

^a Subjects who fail to qualify for the third randomization due to $HbA1c \ge 7.5\%$ at Week 26 may qualify at Week 32 if $HbA1c \le 7.5\%$ at Week 32.

^b Subjects who meet the eligibility criteria at Week 26 will undergo the third randomization at Week 32, and subjects who meet the eligibility criteria at Week 32 will undergo the third randomization at Week 40. Subjects who have passed Week 40 of the study will not be eligible for the third randomization.

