- To assess the percentage of subjects with baseline HbA1c ≥ 7% who achieve an HbA1c level < 7.0% after 52 weeks of oral blinded add-on therapy with dapagliflozin versus placebo or saxagliptin versus placebo in pediatric T2DM subjects with HbA1c of 6.5 to 10.5% on diet and exercise and metformin (IR or XR), insulin, or metformin (IR or XR) plus insulin.
- To assess the effect of monotherapy of dapagliflozin therapy (and separately saxagliptin therapy) for subjects randomized to withdraw background metformin relative to dapagliflozin+metformin (and separately saxagliptin+metformin) and relative to placebo+metformin during the randomized withdrawal period using change in HbA1c, change in FPG, achievement of therapeutic glycemic response (HbA1c < 7%) and time to rescue or discontinuation due to lack of glycemic control.

Pharmacokinetic/Pharmacodynamic Objective:

 To explore the pharmacokinetic (PK) and exposure-response relationship of dapagliflozin and, separately, saxagliptin, and its metabolite 5-hydroxy-saxagliptin (5-OH-saxagliptin), in subjects aged 10 to below 18 years with T2DM based on the collection of population PK samples.

Study Design: The proposed study is a 26-week Phase 3b, multicenter, randomized, placebo-controlled, double-blind, parallel-group study with a 26-week safety extension period to evaluate the safety and efficacy of dapagliflozin (5 mg and 10 mg), and, separately, saxagliptin (2.5 mg and 5 mg) in pediatric subjects with T2DM, and an additional post-study visit at Week 104 for assessment of measures of growth and maturity. Approximately 243 pediatric subjects will be randomized in a 1:1:1 ratio to receive dapagliflozin 5 mg, saxagliptin 2.5 mg, or placebo. Approximately 81 subjects will be randomized to each treatment arm.

The primary efficacy endpoint will be assessed at the end of the initial 26-week double-blind treatment period (referred to as the ST period [from Day 1 to end of Week 26]). The ST period will be followed by a 26-week, double-blind safety extension period (the LT treatment period [from Week 27 to end of Week 52]). Dapagliflozin and, separately, saxagliptin will be compared against the single shared placebo comparator.

Safety monitoring will continue following the Week 52 end-of-treatment visit until the Week 104 post-study visit. Measures of growth and maturity will be assessed at the Week 104 post-study visit.

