8.4.2.3 Exploratory Efficacy Analyses

Exploratory analyses will be performed for overall saxagliptin and overall dapagliflozin separately, by combining all low-dose and high-dose treatment groups as appropriate.

As with the primary and secondary efficacy analyses, separate models will be used for saxagliptin and dapagliflozin analyses, and each analysis will include the (common) placebo group.

Additionally, subjects belonging to the randomization strata of background therapy metformin alone with HbA1c < 7.5% at Week 26 or Week 32 will be eligible for a third randomization:

- Subjects initially randomized to the active arm will be randomized 1:1 to either discontinuing background therapy with metformin or to continuing current treatment. For subjects randomized to withdraw metformin, those receiving the low-dose will be up-titrated to the high-dose whereas those receiving the high-dose will continue on the high-dose.
- These subjects will be used to assess the effect of dapagliflozin (or saxagliptin) monotherapy versus dapagliflozin (or saxagliptin) with metformin add-on therapy. This analysis will estimate the effect of metformin on efficacy in the presence of dapagliflozin (or saxagliptin) and indicate the effects that would be lost/gained if withdrawing metformin (and using only monotherapy).
- Subjects initially randomized to the placebo arm will be randomized 1:1:1 to either discontinue metformin and switch to the dapagliflozin high-dose, or to discontinue metformin and switch to the saxagliptin high-dose, or to continue with their current treatment (placebo+metformin).
- These subjects will be used to assess the effect of dapagliflozin (or saxagliptin) monotherapy versus metformin alone at steady state.

Exploratory efficacy endpoints for short-term assessment of saxagliptin and dapagliflozin

These analyses will be conducted on the Randomized Subjects Data Set.

Comparison of the percentage of subjects who require glycemic rescue medication or discontinue the study medication due to lack of efficacy at or prior to Week 26 will be performed between overall dapagliflozin (or saxagliptin) and placebo.

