The above endpoints will be summarized within each treatment group from the original randomization as follows:

- For subjects initially randomized to the dapagliflozin (or saxagliptin) group, the subjects
 re-randomized to withdraw metformin will be compared to the subjects re-randomized to stay
 on metformin. Separate analyses will be performed for subjects respectively randomized to
 either the dapagliflozin or saxagliptin group.
- For subjects initially randomized to the placebo group, the subjects who were re-randomized
 to switch to dapagliflozin (or saxagliptin) monotherapy will be compared to the subjects who
 were re-randomized to stay on placebo with background metformin. Separate analyses will be
 performed respectively for subjects re-randomized to the dapagliflozin and for those
 re-randomized to the saxagliptin group, using those re-randomized to remain on placebo as
 comparator.

The observed and change from withdrawal baseline in HbA1c and in FPG will be summarized. Percentage of subjects who achieve or maintain an HbA1c level < 7.0% at the end of the withdrawal period will also be summarized.

Time from baseline withdrawal (days) to initiation of glycemic rescue medication or discontinuation of study medication due to lack of efficacy during the randomized withdrawal period will be summarized using Kaplan-Meier estimates.

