4.6 Exploratory efficacy analyses

Exploratory endpoints will not be statistically tested. As with the primary and secondary efficacy analyses, separate models will be used for dapagliflozin and saxagliptin analyses, and each analysis will include the (common) placebo group. Exploratory analyses will be performed for overall dapagliflozin and overall saxagliptin separately, by combining all treatment groups (low-dose and high-dose).

Details are provided below.

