4.6.2.5 Percentage of subjects who initiate glycaemic rescue medication

The number and percentage of subjects who require glycaemic rescue medication during the 52-week treatment period will be provided.

In addition, this analysis will be repeated for the subgroup of subjects on a stable baseline dose of metformin IR or XR (with or without insulin).

4.6.3 Exploratory efficacy analyses for monotherapy assessment during the randomised withdrawal period

These analyses will be conducted during the randomised withdrawal period using the Randomised Withdrawal Subjects Data Set.

The endpoints will be summarised within each treatment group (as defined in Section 2.1) from the original randomisation as follows:

- For subjects initially randomised the dapagliflozin (or saxagliptin) group, the subjects re-randomised to withdraw metformin will be compared to the subjects re-randomised to stay on metformin. Separate analyses will be performed for subjects respectively randomised to either dapagliflozin or saxagliptin group.
- For subjects initially randomised to the placebo group, the subjects who were re-randomised to switch to dapagliflozin (or saxagliptin) monotherapy will be compared to the subjects who were re-randomised to stay on placebo with background metformin. Separate analyses will be performed respectively for subjects re-randomised to

dapagliflozin and for those re-randomised to saxagliptin, using the those re-randomised to placebo as comparator.

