4.6.3.1 Observed and change from withdrawal baseline in HbA1c and FPG

Descriptive summaries of observed and change from withdrawal baseline in HbA1c and, separately, FPG for withdrawal baseline and post-withdrawal baseline visits will be provided. This analysis will include all data regardless of rescue medication initiation or adherence. No imputation will be performed.

4.6.3.2 Percentage of subjects who achieve or maintain a HbA1c level < 7% at the end of the withdrawal period

The number and percentage of subjects who achieve or maintain a HbA1c level < 7% at the end of the withdrawal period will be provided. This analysis will include all data regardless of rescue medication initiation or adherence. No imputation will be performed.

4.6.3.3 Time to glycaemic rescue medication or discontinuation of study medication due to lack of efficacy

A time-to-event analysis (where event is first use of rescue medication or discontinuation of study medication due to lack of efficacy, whichever is earlier) during the 52-week treatment period will be analysed. Date of first dose will be date of first dose in the randomised withdrawal period. Kaplan-Meier estimates will be calculated, and 95% CIs will be presented. No Kaplan-Meier plot will be presented for this analysis.

Rules for censoring are described in Section 4.1.11.

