		Without considering the third randomisation (up to Week 52)	Excluding subjects randomised to withdrawal (up to Week 52)
	discontinuing study medication due to lack of efficacy	Randomised Subjects Dataset	
		E2 Kaplan-Meier Randomised Subjects Dataset	
	Percentage of subjects who initiate rescue medication at Week 52	E2, supportive Descriptive statistics Randomised Subjects Dataset	
		E2, subpopulation Descriptive statistics Randomised Subjects Dataset	

E=Exploratory.

Subpopulation: subgroup of subjects on background medication metformin +/- insulin.

Randomised withdrawal period

Parameter	Assessment	For subjects initially randomised the dapagliflozin (or saxagliptin) group: Dapagliflozin (or saxagliptin) vs Dapagliflozin (or saxagliptin) + Metformin	For subjects initially randomised to the placebo group: High-dose dapagliflozin (or saxagliptin) vs Placebo + Metformin
HbA1c	Mean change from withdrawal baseline to Week 52	E5 Descriptive statistics No imputation Randomised Withdrawal Subjects Dataset	E5 Descriptive statistics No imputation Randomised Withdrawal Subjects Dataset
	Percentage of subjects who achieve an HbA1c level < 7% at Week 52	E5, supportive Descriptive statistics No imputation Randomised Withdrawal Subjects Dataset	E5, supportive Descriptive statistics No imputation Randomised Withdrawal Subjects Dataset
FPG	Mean change from withdrawal baseline to Week 52	E5 Descriptive statistics No imputation Randomised Withdrawal Subjects Dataset	E5 Descriptive statistics No imputation Randomised Withdrawal Subjects Dataset

Parameter	Assessment	For subjects initially randomised the dapagliflozin (or saxagliptin) group: Dapagliflozin (or saxagliptin) vs Dapagliflozin (or saxagliptin) + Metformin	For subjects initially randomised to the placebo group: High-dose dapagliflozin (or saxagliptin) vs Placebo + Metformin
Glycaemic rescue medication or discontinuing study medication due to lack of efficacy	Time to Glycaemic rescue medication or discontinuing study medication due to lack of efficacy	E5, supportive Kaplan-Meier Randomised Withdrawal Subjects Dataset	E5, supportive Kaplan-Meier Randomised Withdrawal Subjects Dataset
	Percentage of subjects who initiate rescue medication at Week 52	E5, supportive Descriptive statistics No imputation Randomised Withdrawal Subjects Dataset	E5, supportive Descriptive statistics No imputation Randomised Withdrawal Subjects Dataset

E=Exploratory.

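### The randomised-withdrawal objective is a relative effect on HbA1c and FPG, but both documents plan only per-group summaries, with no between-group difference or interval

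*Protocol*

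**What the plan says.** The objective is relative: "To assess the effect of monotherapy of dapagliflozin therapy (and separately saxagliptin therapy) for subjects randomized to withdraw background metformin relative to dapagliflozin+metformin", and also relative to placebo plus metformin. Its listed measures are change in HbA1c, change in FPG, HbA1c below 7%, and time to rescue or discontinuation for lack of glycaemic control.

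Protocol 8.4.2.3 states the purpose in the same terms: "This analysis will estimate the effect of metformin on efficacy in the presence of dapagliflozin (or saxagliptin". For the method, the same section says only: "The observed and change from withdrawal baseline in HbA1c and in FPG will be summarized".

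SAP 4.6.3 repeats the comparative intent for the active arms, where subjects "re-randomised to withdraw metformin will be compared to the subjects re-randomised to stay on metformin". It has a parallel statement for the placebo arm. The methods that follow are these:

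- SAP 4.6.3.1: "Descriptive summaries of observed and change from withdrawal baseline in HbA1c and, separately, FPG for withdrawal baseline and post-withdrawal baseline visits will be provided", regardless of rescue and without imputation.
- SAP 4.6.3.2: "The number and percentage of subjects who achieve or maintain a HbA1c level < 7% at the end of the withdrawal period will be provided".
- SAP 4.6.3.3: Kaplan-Meier estimates with 95% CIs.
- SAP 4.6.3.4: number and percentage rescued.
- SAP 8.14, Table 23 (E5): "Mean change from withdrawal baseline to Week 52", as descriptive statistics without imputation.

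SAP 4.6 adds the general rule: "Exploratory endpoints will not be statistically tested".

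**The concern.** Two columns of means and SDs are not an estimate of an effect. HbA1c may drift over the withdrawal period whether or not metformin is stopped, so the change within one group mixes that drift with the effect of withdrawal. Only the difference between randomised groups separates the two, and only an interval shows how well the data determine it.

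The groups are likely to be small. Entry to the third randomisation needs metformin-only background treatment, HbA1c below 7.5% at Week 26 or 32, no rescue and continued study drug, out of about 81 children per Day 1 arm. For children recruited before a site implemented the third amendment, taking part was optional. Two similar means from such groups could be read as showing that metformin can be stopped without loss of control, and two different means as showing the reverse, when the data may support neither. Metformin is withdrawn by randomisation in this period to learn this effect, so the plan should report it with its uncertainty.

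**Working it through.** **1. The plan's own figure.** The only design calculation is for the primary endpoint (Protocol 8.1, SAP 1.3): 81 per arm, difference 0.75, SD 1.7, two-sided alpha 0.05. Power = Φ(0.75 / (1.7 × √(2/81)) − 1.96) = Φ(2.81 − 1.96) = 0.80, which reproduces the stated figure of about 80%. No size or precision is given for the withdrawal period.

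**2. Objective against planned output.**

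| Measure in the objective | Planned output (SAP) | Contrast between groups? |
|---|---|---|
| Change in HbA1c, change in FPG | 4.6.3.1: descriptive summary, which SAP 4.1.2 defines as n, mean, SD, median, minimum, maximum | None |
| HbA1c below 7% | 4.6.3.2: number and percentage | None |
| Time to rescue or discontinuation | 4.6.3.3: Kaplan-Meier with 95% CIs | None; the CIs are for each group's event probability |

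SAP 4.1.11 mentions a pairwise log-rank test, but 4.6.3.3 cites that section only for censoring. Unlike 4.6.1.2 and 4.6.2.4, it names neither a log-rank test nor a Cox model.

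**3. Could another analysis supply the contrast?** The Week 52 analysis in SAP 4.6.2.1 gives an ANCOVA difference with 95% CIs, but between the Day 1 drug and placebo arms. Its weighted version (SAP 4.6.2) gives children who withdrew metformin a weight of zero. Neither version can answer the withdrawal question.

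**4. Size of the unreported uncertainty.** Half-width = t(0.975, 2n − 2) × SD × √(2/n). The group size n is not in the documents and is assumed. An SD of 1.7 is documented for the primary endpoint only; 1.0 is an assumed lower value.

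| Contrast | n per group | t | SD 1.0 | SD 1.7 |
|---|---|---|---|---|
| Within a drug arm (1:1) | 5 | 2.306 | 1.46 | 2.48 |
| | 10 | 2.101 | 0.94 | 1.60 |
| | 15 | 2.048 | 0.75 | 1.27 |
| | 20 | 2.024 | 0.64 | 1.09 |
| Within the placebo arm (1:1:1, pairwise) | 3 | 2.776 | 2.27 | 3.85 |
| | 6 | 2.228 | 1.29 | 2.19 |
| | 10 | 2.101 | 0.94 | 1.60 |

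Values are percentage points of HbA1c. Most exceed the 0.75 used to size the primary comparison, but not all: 20 per group with SD 1.0 gives 0.64.

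**5. Does baseline adjustment narrow the interval?** Let ρ be the correlation between withdrawal baseline and Week 52, and k the ratio of baseline SD to Week 52 SD. In large samples, the variance of the ANCOVA difference relative to that of raw change is (1 − ρ²) / (1 + k² − 2ρk).

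- k = 1: the ratio reduces to (1 + ρ)/2. Width ratios are 0.81, 0.87 and 0.92 for ρ = 0.3, 0.5 and 0.7.
- k = 0.5: width ratios are 0.98, 1.00 and 0.96.

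The HbA1c limit of 7.5% at entry makes a k below 1 plausible. In small groups the extra model terms also cost degrees of freedom. A simulation with 6 per group, k = 1, both a baseline and a week-of-entry term, and an assumed 30% entering at Week 40 gave ratios of about 0.93, 1.00 and 1.06. A gain in precision therefore cannot be relied on.

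**The case against.** The strongest reply is that descriptive reporting is a declared choice. These endpoints are exploratory, SAP 4.6 rules out testing them, and the protocol's own method wording is summary only. The SAP is also cautious elsewhere about small groups: SAP 4.4.3.1 withholds adjusted estimates and differences when a subgroup category has fewer than 10 children in any treatment group. The Week 52 ANCOVA uses arms of about 81, so it is not a like-for-like precedent. Finally, n, mean and SD let a reader compute an unadjusted difference and interval.

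Much of this stands. It removes any case for a test, and it argues against a model in very small groups. It does not explain why an objective stated as a contrast has no contrast in its output. An interval is not a test, and the Week 52 endpoints, equally exploratory, receive one. Self-computation is also uncertain. SAP Table 12 says the withdrawal treatments are combined into one table, and the Appendix 8.13 monotherapy labels pool placebo switchers with children who started on active drug, whereas Table 23 keeps the originating arms apart.

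Four stronger readings are tempting, and the documents do not support them:

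- **The SAP departs from the protocol.** It does not. The gap between objective and method is in both documents.
- **Nothing but raw change is planned.** Percentages and Kaplan-Meier estimates are planned too. They simply lack a contrast.
- **Pooling children randomised at Week 32 and Week 40 is a flaw.** Entry week is balanced in expectation by randomisation, and the protocol keeps at least 12 weeks before Week 52. Pooling does not bias the comparison.
- **Adjustment would clearly tighten the interval.** Step 5 shows that it may not.

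One further caution is correct. The difference would not isolate metformin. Children on the low dose who withdraw metformin also move to the high dose, while their comparators keep their current dose, and withdrawal is open-label.

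**Conclusion.** The point holds for change in HbA1c and FPG. The objective is a relative effect, both documents announce a comparison, and neither specifies a difference or an interval for it. It should be corrected, but it is confined to exploratory reporting and touches no confirmatory claim.

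That conclusion rests on the text alone. The half-widths in step 4 only illustrate what an interval might show, and they depend on the assumed group size and SD. What they indicate is limited precision, which is a reason to print the interval.

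**What to change.** In SAP 4.6.3.1 and Table 23 (E5), for each contrast listed in 4.6.3 and within the originating Day 1 arm, add the difference in mean change from withdrawal baseline to Week 52 in HbA1c and in FPG, with a nominal 95% CI and no test. Keep the descriptive tables.

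- Adjust for the withdrawal-baseline value when each group has at least 10 children, in line with SAP 4.4.3.1. Otherwise report the unadjusted difference. A factor for week of third randomisation (32 or 40) is optional.
- Label the estimate as the effect of the withdrawal strategy, because of the accompanying dose change, and as regardless of rescue and without imputation.

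The cost is a few model runs and table rows, some with wide intervals. No new data are needed and the multiplicity plan is unchanged.
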